|------------|-----------------|-----|----|
| I IOUKL I. | 510D1 5CHEMATIC | . 4 | ·T |

LIST OF ABBREVIATIONS AND DEFINITIONS OF TERMS

AE Adverse Event

ASA Acetylsalicylic Acid

BID Twice Daily
°C Degrees Celsius

CME Cystoid Macular Edema

CRF Case Report Form

CRO Contract Research Organization

EE Efficacy Evaluable

eCRF Electronic Case Report Form

°F Degrees Fahrenheit

FDA Food and Drug Administration

GCP Good Clinical Practice

HIPAA Health Insurance Portability and Accountability Act

ICH International Conference on Harmonization

ID IdentificationIOL Intraocular LensIOP Intraocular Pressure

IRB Institutional Review Board

ITT Intent-to-Treat
IUD Intrauterine device

KPI Kala Pharmaceuticals, Inc. LE Loteprednol etabonate

MedDRA Medical Dictionary for Regulatory Activities

mg Milligram
mL Milliliter
mm Millimeter

mmHg Millimeter of Mercury
MAR Missing at random

MPP Mucus Penetrating Particles

NDA New Drug Application

NSAIDs Non-steroidal Anti-inflammatory Drugs

OTC Over the Counter

PDF Portable Document Format

pH Potential Hydrogen SAE Serious Adverse Event

SAR Suspected Adverse Reaction SLT Selected Laser Trabeculoplasty

TNF Tumor Necrosis Factor

UPT Urine Pregnancy Test
US United States of America

VA Visual Acuity

WOCBP Women of Child Bearing Potential

w/v Weight to Volume

1. INTRODUCTION

Intraocular inflammation is an anticipated sequela of intraocular surgery such as cataract removal and intraocular lens (IOL) placement. In general, trauma to the internal structures of the eye is accompanied by the production of prostaglandins and other vasoactive moieties, an increase in blood flow to the affected area, and extravasations of protein and cellular blood elements. Postoperative inflammation is manifested principally as bulbar erythema, corneal edema, ciliary flush and aqueous cells and flare.

If left untreated, inflammation generally resolves within 2 to 4 weeks after surgery; however 20% to 80% of patients present with anterior chamber cells and/or flare 2 weeks after cataract surgery and IOL placement. Since untreated intraocular inflammation following cataract surgery may lead to complications such as cystoid macular edema (CME) (Apple et al., 1992; Tennant, 1978), treatment with anti-inflammatory agents such as glucocorticosteroids is employed to reduce pain and discomfort, and to facilitate recovery of the blood-aqueous barrier. When administered at the time of surgery and during the immediate postoperative period, glucocorticosteroids can reverse the clinical and non-clinical manifestations of inflammation (Leopold, 1985). In the United States (US), topical glucocorticosteroids are routinely prescribed for at least 2 weeks following cataract surgery, with longer treatment prescribed in cases of severe or unremitting inflammation.

Loteprednol etabonate (LE) is an ester corticosteroid that is rapidly metabolized to inactive metabolites, and has been reported to have fewer side effects than traditional glucocorticosteroids. Loteprednol etabonate was approved by Food and Drug Administration (FDA) in 1998 under New Drug Application (NDA) 20-583 (Lotemax®; Bausch & Lomb). Lotemax has gained wide acceptance by ophthalmologists for use in the treatment of postoperative ocular inflammation. Despite its attractive pharmacologic activity, wherein the drug is active at the site of administration but is rapidly metabolized to an inactive compound following absorption, Lotemax requires frequent dosing (four times per day) which may reduce patient compliance.

Kala Pharmaceuticals, Inc. has developed an improved formulation of loteprednol etabonate, designated as KPI-121, using a proprietary technology known as Mucus Penetrating Particles (MPP). MPP technology utilizes submicron drug particles formulated to enhance penetration through the mucous layer of the tear film. KPI-121 is an aqueous suspension of submicron particles of loteprednol etabonate formulated with excipients present in other FDA-approved ophthalmic investigational products. Preclinical studies have shown improved pharmacokinetics for KPI-121 compared to Lotemax, with prolonged drug presence on the ocular surface and increased drug penetration into ocular tissues. This improved

pharmacokinetic profile has the potential to reduce either dosing strength or frequency of loteprednol etabonate as compared to Lotemax.

Kala Pharmaceuticals, Inc. intends to develop KPI-121 for the treatment of postoperative inflammation and pain following ocular surgery.

1.1. DESCRIPTION OF INVESTIGATIONAL PRODUCT

KPI-121 contains submicron particles of loteprednol etabonate suspended in a formulation consisting of excipients that have been used in other FDA-approved ophthalmic products. Kala is developing this improved loteprednol etabonate formulation for the treatment of postoperative anterior segment inflammation and pain.

KPI-121 is a sterile, aqueous submicron suspension of loteprednol etabonate and will be filled in a white, low-density polyethylene plastic bottle with a translucent, controlled-drop polypropylene tip, a pink polypropylene cap and a white polyethylene tamper-evident overcap. The bottle will be a 5 mL dropper bottle with a nominal fill of 3.2 mL.

For this trial, KPI-121 investigational product will be supplied as 1.0% ophthalmic suspension. Each mL of KPI-121 1.0% ophthalmic suspension contains 10 mg loteprednol etabonate as the active ingredient. Inactive ingredients in KPI-121 investigational product are

preservative. KPI-121 1.0% ophthalmic suspension is essentially isotonic and is buffered to maintain a power of hydrogen (pH) of 5.0 - 7.0.

The placebo control has the same excipient composition as KPI-121 1.0% ophthalmic suspension but does not contain loteprednol etabonate. The placebo control contains

as

preservative. The placebo control is essentially isotonic and buffered to maintain pH 5.0-7.0. It is a sterile, aqueous solution supplied in the same white, low-density polyethylene plastic bottle with the same translucent, controlled-drop polypropylene tip, pink polypropylene cap and white polyethylene tamper-evident overcap as KPI-121 1% ophthalmic suspension investigational product.

1.2. JUSTIFICATION FOR ROUTE OF ADMINISTRATION AND DOSE SELECTION

KPI-121 1.0% will be administered as a topical ophthalmic suspension.

Subjects are expected to self-administer one to two drops of either KPI-121 1.0% ophthalmic suspension or placebo control BID.

Direct instillation is the most efficient method for delivery to the ocular surface and is an accepted and widely used method for topical application to the eye. This study will examine effect and tolerability for 14 days of KPI-121 1.0% ophthalmic suspension dosed BID.

For additional details on the toxicology studies and the respective safety multiples, see the Investigator's Brochure.

1.3. GCP COMPLIANCE

This clinical trial will be conducted in compliance with the protocol, International Conference on Harmonization (ICH) guidelines, Good Clinical Practices (GCP) guidelines and other applicable regulatory requirements.

1.4. POPULATION TO BE STUDIED

Approximately 720 subjects who are candidates for cataract surgery will be screened. One study eye from approximately 500 subjects who have undergone routine, uncomplicated cataract surgery and have ≥ 2 anterior chamber cells in the study eye at Visit 3 (Day 1) will be evaluated at approximately 35 centers located in the US.

2. TRIAL OBJECTIVES AND PURPOSE

2.1. OBJECTIVE

The primary objective of this study is to investigate the safety and efficacy of KPI-121 1.0% ophthalmic suspension compared to placebo in subjects who have undergone cataract surgery.

3. TRIAL DESIGN

3.1. PRIMARY EFFICACY ENDPOINTS

The primary endpoints of this study will be evaluated using hierarchical statistical testing in the following sequence:

- 1. Proportion of study eyes with complete resolution of anterior chamber cells (grade = 0) at Visit 5 (Day 8 ± 1 day) maintained through Visit 6 (Day 15 ± 1 day) without receiving rescue medication prior to Visit 6 (Day 15 ± 1 day) as compared between KPI-121 1.0% ophthalmic suspension dosed BID and placebo dosed BID.
- 2. Proportion of study eyes with complete resolution of pain (grade = 0) at Visit 5 (Day 8 ± 1 day) maintained through Visit 6 (Day 15 ± 1 day) without receiving rescue medication prior to Visit 6 (Day 15 ± 1 day) as compared between KPI-121 1.0% ophthalmic suspension dosed BID and placebo dosed BID.

3.2. SECONDARY EFFICACY ENDPOINTS

- Proportion of study eyes with complete resolution of ocular pain (grade = 0) at Visit 4
 (Day 4 ± 1 day) maintained through Visit 6 (Day 15 ± 1 day) without receiving rescue
 medication prior to Visit 6 (Day 15 ± 1 day) as compared between KPI-121 1.0%
 ophthalmic suspension dosed BID and placebo dosed BID. This endpoint will be tested at
 α = 0.0167.
- 2. Proportion of study eyes with complete resolution of anterior chamber flare (grade = 0) at Visit 4 (Day 4 ± 1 day) maintained through Visit 6 (Day 15 ± 1 day) without receiving rescue medication prior to Visit 6 (Day 15 ± 1 day) as compared between KPI-121 1.0% ophthalmic suspension dosed BID and placebo dosed BID. This endpoint will be tested at $\alpha = 0.0167$.
- 3. Change from baseline in mean anterior chamber cell count at Visit 4 (Day 4 ± 1 day) as compared between KPI-121 1.0% ophthalmic suspension dosed BID and placebo dosed BID. This endpoint will be tested at $\alpha = 0.0167$.

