4.3. RANDOMIZATION CRITERIA

To qualify for randomization at Visit 3 (Postoperative Day 1), a subject must:

- 1. Have undergone routine, uncomplicated cataract surgery (e.g., phacoemulsification with posterior chamber IOL implantation, not combined with any other surgery).
- 2. Have \geq Grade 2 anterior chamber cells.
- 3. Continue to meet inclusion/exclusion criteria with respect to current ocular and medical conditions (Section 4.1 and Section 4.2), and must not have taken prohibited medications (Section 6.2.2).

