5.1.3. Visit 3: Randomization Visit (Day 1)

The randomization visit will occur 1 day after Visit 2/Surgery Visit. This visit should be scheduled in the morning (if possible) to allow for administration of two doses of investigational product during the day for eligible subjects.

Eligible subjects who meet the randomization criteria (Section 4.3) will continue in the study.

The following will be performed/assessed (**NOTE:** All ocular assessments must be performed in both eyes):

- Obtain Subject-Rated Ocular Pain Assessment
- Review use of any concomitant medications since the last visit
- Assess occurrence of any AEs since the last visit (**NOTE**: Expected changes or the presence of inflammation resulting from routine uncomplicated cataract surgery will not be captured as AEs.)
- Perform:
 - Snellen Distance VA by pinhole method
 - o Slit Lamp Biomicroscopy

CONFIDENTIAL

- Signs of anterior ocular inflammation (cell and flare grading)
- Palpebral conjunctival erythema, corneal edema, hyphema, ciliary flush, bulbar conjunctival injection
- IOP Measurement

Upon verification of study eligibility (Section 4.3), eligible subjects will be randomized to receive either KPI-121 1.0% ophthalmic suspension dosed BID or placebo dosed BID. The following will be performed for all randomized subjects:

- Administer the first dose of double-masked investigational product in the clinic under the supervision of designated study personnel.
- Prior to administration of investigational product, remind the subjects regarding the proper method for instillation including but not limited to shaking investigational product bottle prior to each instillation.
- Since subjects will receive one dose of investigational product in the clinic, instruct the subject to self-administer one additional dose of investigational product on the first day.
- Assess the occurrence of any AEs after investigational product administration
- Dispense investigational product kits and instructions for administration
- Schedule subjects to return for Visit 4 on Day 4 ± 1 day.

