If this test is statistically significant at the two-sided $\alpha = 0.05$ level in favor of the KPI-121 1.0% ophthalmic suspension group, then the difference in the proportion of study eyes with complete resolution of pain (grade = 0) at Visit 5 (Day 8 ± 1 day) maintained through Visit 6 (Day 15 ± 1 day) without receiving rescue medication prior to Visit 6 (Day 15 ± 1 day) as compared between KPI-121 1.0% ophthalmic suspension dosed BID and placebo dosed BID will be tested using the same statistic.

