9.3. LEVEL OF SIGNIFICANCE

The primary assessment will be evaluated using a 5% level of significance using the hierarchical testing described in Section 9.1.2 Analysis of Efficacy.

All other reported p-values will be considered descriptive and hypothesis generating.

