APPENDIX 4: SLIT LAMP BIOMICROSCOPY

The biomicroscopy exam will be performed at every visit (except Visit 2/Surgery) with the slit lamp using a beam of 1.0 mm height and 1.0 mm width with the beam at maximum luminance and using the high powered lens if using Haag-Streit model slit lamp. If alternate model used, site to assure a 1.0 mm by 1.0 mm window with high magnification is achieved.

This procedure will be the same for all subjects observed at the Investigator's site.

Anterior Chamber

Cells

0 = No cells seen

1 = 1 - 5 cells

2 = 6 - 15 cells

3 = 16 - 30 cells

4 =greater than 30 cells

Flare

0 = None

1 = Mild (trace to clearly noticeable, visible)

2 = Moderate (without plastic aqueous humor)

3 = Marked (with plastic aqueous humor)

4 = Severe (with fibrin deposits and/or clots)

Hyphema:

0 = Absent

1 = Mild

2 = Moderate

3 = Severe

Conjunctiva

Bulbar Conjunctival Injection

- 0 = Absent
- 1 = Mild
- 2 = Moderate
- 3 = Severe

Palpebral Conjunctival Erythema

- 0 = Absent
- 1 = Mild
- 2 = Moderate
- 3 = Severe

Cornea

Edema

- 0 = Absent
- 1 = Mild
- 2 = Moderate
- 3 = Severe

Sclera

Ciliary Flush

- 0 = Absent
- 1 = Mild
- 2 = Moderate
- 3 = Severe

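### Flare secondary: an eye with no flare at Day 1 can count as resolved, and no described analysis uses the flare grade taken before the first dose

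*Combined protocol and SAP*

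**What the plan says.** - **Endpoint.** Protocol Section 3.2 (and the Synopsis) defines secondary endpoint 2 as the "Proportion of study eyes with complete resolution of anterior chamber flare (grade = 0) at Visit 4", maintained through Visit 6 without rescue before Visit 6. Each secondary carries an error level: "This endpoint will be tested at α = 0.0167".
- **Entry.** Section 4.3 requires at least "Grade 2 anterior chamber cells" at Visit 3. It sets no flare condition in either direction.
- **Baseline measurement.** Section 5.1.3 lists "Signs of anterior ocular inflammation (cell and flare grading") among the Visit 3 assessments. Only after eligibility is verified and the subject is randomized does it say to "Administer the first dose of double-masked investigational product in the clinic under the supervision of designated study personnel". Appendix 4 scores flare on its own 0 to 4 scale, separate from cells: 0 is none, and the next step is "1 = Mild (trace to clearly noticeable, visible").
- **Analysis.** Section 9.1.2 gives an unadjusted chi-square for the first primary endpoint (cells) and says the second primary (pain) "will be tested using the same statistic". No test is named for the secondaries. No baseline covariate or stratification factor appears anywhere.
- **Status.** Section 9.3 says "All other reported p-values will be considered descriptive and hypothesis generating", which does not sit easily with an assigned alpha of 0.0167.

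**The concern.** For cells, the entry rule guarantees that every randomized eye has something to resolve. For flare it does not. An eye without flare on Day 1 that stays at grade 0 through Visit 6, unrescued, is a success in either arm.

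Two things follow. First, the resolution rate mixes eyes whose flare cleared with eyes that had none at baseline, so it is hard to read as a rate of resolution. Second, the Visit 3 flare grade is a true baseline measure, is already collected, and plausibly predicts flare three days later. Leaving it out may cost precision, and any chance imbalance in flare-free eyes stays inside the estimated difference.

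**Working it through.** **1. The plan's own figure.** Section 9.2 states 99% power for 0.31 v 0.15, 250 per group, two-sided 0.05 (cells; no figure is given for flare). With d the difference, p̄ the mean rate and n = 250:

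power = Φ{ [d − z·√(2p̄(1−p̄)/n)] / √([p1(1−p1) + p2(1−p2)]/n) }

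Here d = 0.16 and p̄ = 0.23. The null standard error is √(2×0.23×0.77/250) = 0.03764, and the alternative is √((0.2139+0.1275)/250) = 0.03695. With z = 1.960: (0.16 − 0.0738)/0.03695 = 2.33, power 0.990. The stated figure reproduces.

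**2. The same formula at alpha 0.0167** (sidedness is not stated; two-sided assumed, z = 2.393), unadjusted:
- 0.31 v 0.15: (0.16 − 0.0901)/0.03695 = 1.89, power 97%.
- 0.25 v 0.15: (0.10 − 0.0856)/0.0355 = 0.41, power 66%.
- 0.35 v 0.25: (0.10 − 0.0981)/0.0407 = 0.05, power 52%.

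The last two pairs are assumed moderate effects. The first borrows the cell rates.

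**3. Stratified test, model A.** Day 1 flare has three strata (0 / 1 / 2 or more). The stratum log-odds offsets are the same in both arms, and intercepts are solved so that the overall rates are as stated. The test is Cochran-Mantel-Haenszel (CMH):

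z = Σ(a − n_T·m/N) / √Σ[n_T·n_C·m(N−m) / (N²(N−1))]

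In each stratum, a is the active successes, m all successes, n_T and n_C the arm sizes, and N their sum. Simulation used 60,000 trials per scenario. Strata were 20/50/30% or 30/50/20%.

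| Offsets | 0.25 v 0.15: raw → CMH | 0.35 v 0.25: raw → CMH |
|---|---|---|
| 1, 0, −1 | 66% → 69–70% | 52% → 56–57% |
| 2, 0, −1 | 66% → 76–77% | 52% → 64–65% |
| 2.5, 0, −1.5 | 66% → 81–83% | 52% → 71–72% |

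- Overall rates of 0.31 v 0.15: 97% raw, gain at most about 2.5 points in any of these scenarios.
- Only 5% flare-free (5/55/40) with the mildest offsets: 66% → 68% and 52% → 55%.
- Uninformative baseline flare: loss of about 0.5 points or less.

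**4. Model B.** Here the rates 0.31 v 0.15 apply only to eyes *with* Day 1 flare. A share f starts at grade 0 and succeeds at 0.8 in both arms. The overall difference becomes 0.16×(1−f): 0.144 at f = 10% and 0.112 at f = 30%. CMH is stratified as grade 0 v above 0 (40,000 trials).

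| f | Raw | CMH |
|---|---|---|
| 0% | 97% | 97% |
| 5% | 93.5% | 95.5% |
| 10% | 88% | 93% |
| 20% | 73% | 86% |
| 30% | 56% | 74% |

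The gains exceed the 2.5 points of model A because the overall difference here is diluted below 0.16. With the grade-0 success rate varied from 0.6 to 0.9, the gain is 2 to 7 points at f = 10% and 7 to 25 at f = 30%.

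**5. Interpretation.** In model B at f = 20%, the placebo success rate is 0.20×0.80 + 0.80×0.15 = 0.16 + 0.12 = 0.28. So 0.16/0.28 = 57% of placebo successes would be eyes with no flare at Day 1.

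**6. Validity.** Under no treatment effect (model B), the raw test rejects in 0.016 to 0.017 of trials against a nominal 0.0167.

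**The case against.** The strongest reply is that nothing is broken. Randomization balances Day 1 flare in expectation, the unadjusted test's error rate already covers chance imbalance, and an unadjusted comparison of proportions is standard. This stands: the point concerns precision and meaning, not validity.

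Several stronger readings are tempting and are not supported:

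- *That the plan prescribes a raw chi-square for flare.* It does not. Section 9.1.2 assigns chi-square to the two primaries only, and Section 9.5 refers to a statistical analysis plan that could add detail. What can be said is that nothing supplied names a test or a baseline term for the secondaries.
- *That flare must be absent at entry.* Section 4.3 is silent on flare; it neither requires nor excludes it.
- *That Day 1 flare is a strong covariate.* The documents give no flare rates, no Day 1 distribution and no correlation with outcome. If few eyes start clear and the grade predicts little, the gain is 2 to 3 points or less.
- *That flare-free eyes carry no treatment information.* The endpoint requires staying at grade 0 through Visit 6 without rescue, so such an eye can fail, and staying clear may reflect treatment. In model A at 0.25 v 0.15 (20/50/30, offsets 2, 0, −1), flare-free eyes succeed at 0.64 v 0.45 and contribute 0.20×0.19 = 0.038 of the 0.10 difference. Model B sets that contribution to zero, and stratifying still gains.

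The endpoint is also secondary. If Section 9.3 governs, power at 0.0167 has no confirmatory role. The conflict with Section 3.2 needs reconciling separately; under either reading the estimate and interval can benefit.

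**Conclusion.** The point holds as an inexpensive improvement to a secondary endpoint. It does not show an error in a test, bias or an inflated type I error.

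What follows from the documents alone: an eye with no flare on Day 1 can be counted as resolved, the Day 1 grade is available before dosing, and no described analysis uses it.

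What rests on assumption is the size. For stated overall rates, 250 per arm and two-sided alpha 0.0167, the gain is about 2 to 3 points in the mild 5% case, about 3 to 20 points for the moderate effects with 20 to 30% flare-free, and at most about 2.5 points at 0.31 v 0.15. The downside is about 0.5 points. The gain in clarity from separating the two kinds of success does not depend on the power figures, but it matters little if almost every eye has flare on Day 1.

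**What to change.** In Section 9.1.2, before the treatment code is released:

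1. Name a Cochran-Mantel-Haenszel test stratified by Visit 3 flare grade (0 / 1 / 2 or more) for secondary endpoint 2, and state its sidedness.
2. Report the stratum-weighted difference in proportions with its confidence interval.
3. Tabulate responders by arm and Visit 3 flare grade, so that eyes at grade 0 on Day 1 are shown apart from eyes whose flare resolved.

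The cost is a few lines of analysis text and one table, with no new data or visits. The same approach could be used for pain, by Visit 3 pain grade: pain is also rated at that visit and has no entry threshold.

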3.3. SAFETY ENDPOINTS

- Assessment of AEs
- Snellen Distance VA by pinhole method
- Slit Lamp Biomicroscopy
- IOP Measurement
- Dilated Ophthalmoscopy
- Change from baseline to each post-surgery visit in ocular signs:

- o Palpebral conjunctival erythema
- o Corneal edema
- o Hyphema
- Ciliary flush
- o Bulbar conjunctival injection

3.4. DESCRIPTION OF TRIAL DESIGN

This is a Phase 3, multicenter, double-masked, randomized, placebo-controlled, parallel-group study designed to evaluate the safety and efficacy of KPI-121 1.0% ophthalmic suspension versus placebo in subjects who require treatment of postoperative anterior ocular inflammation. Approximately 720 subjects who are candidates for cataract surgery will be screened and approximately 500 subjects who, after undergoing routine, uncomplicated cataract surgery, present at Visit 3 (Day 1) with \geq 2 anterior chamber cells in the study eye will be randomized in this study at approximately 35 centers located in the US.

Subjects who experience postoperative inflammation on the first day following routine, uncomplicated, cataract surgery and who meet all other eligibility criteria will be randomized to one of two study groups in an approximate 1:1 ratio:

- KPI-121 1.0% ophthalmic suspension, BID
- Placebo, BID

Dosing of investigational product will be initiated on the day following surgery, instilled as 1-2 drops in the study eye BID for 14 ± 1 days. The first dose of investigational product will be administered by the subject under the supervision of a designated study team member who is otherwise uninvolved in the assessment or evaluation of the subject. Except for this investigational product administration, no other information or discussion regarding the subject's assigned investigational product will be exchanged, in order to maintain the masking for this trial.

This study will include up to 7 clinic visits (including the surgery day) over 18 to 33 days total study duration. Visit 1 (Screening) will occur between 14 to 1 day(s) prior to surgery and subjects who meet preoperative screening inclusion/exclusion criteria will be entered into the study. At Visit 2 (Surgery/Day 0), subjects will undergo routine cataract surgery according to the Investigator's normal procedures. Visit 3 (Randomization/Day 1) will occur on the day following surgery. Subjects who meet the qualifying postoperative randomization criteria will be eligible for randomization to one of the two study groups and will initiate dosing with investigational product on that day. Following randomization, subjects will be instructed to instill investigational product in the study eye two times a day (BID) for 14 ± 1 days, up until

Visit 6, and return to the clinic to be evaluated at Visit 4 (Day 4 ± 1 day), Visit 5 (Day 8 ± 1 day), and Visit 6 (Day 15 ± 1 day/ End of Investigational Product Use Visit). Subjects will be asked to return to the clinic for Visit 7 (Day 18 ± 1 day) for follow-up and then will be released from the study.

A summary of events is provided in Appendix 1. Procedures and assessments in this study will include:

- Routine uncomplicated cataract surgery
- Subject-Rated Ocular Pain Assessment (Appendix 2)
- Snellen Distance VA by Pinhole Method (Appendix 3)
- Slit Lamp Biomicroscopy (Appendix 4):
 - o Signs of anterior ocular inflammation (cell and flare grading)
 - Palpebral conjunctival erythema, corneal edema, hyphema, ciliary flush, bulbar conjunctival injection
- IOP Measurement (Appendix 5)
- Dilated Ophthalmoscopy (Appendix 6)
- Rescue Therapy Assessment
- Concomitant Medication Use Assessment
- Dosing Compliance Assessment
- Assessments of AEs

A study schematic follows (Figure 1).

[figure not shown]

FIGURE 1: STUDY SCHEMATIC

